- Groups A1 and A2 (Normal): patients with normal liver function will be included in this study as matching control patients (Group A1 for Group B and Group A2 for Group C). If the dose for moderate hepatic impairment group (Group C) is selected to be the recommended clinical dose of 100 mg QD, the control group A2 will not be needed to be enrolled. There will be no control group designated to match severe group. However, if a decision has been made to use the same dose for severe and moderate patients, the half of the control Group A2 will be matching Group C and half will be matching Group D.

Child-Pugh scores (criteria listed in Appendix 3) will be calculated and recorded as part of the liver function testing prior to the start of the first lorlatinib dose, but will not be used to stratify patients into treatment groups.

The enrollment of approximately 76 advanced cancer patients is anticipated in this study in order to have 8 PK-evaluable patients in each of Groups A1, A2, B and C, and 6 PK-evaluable patients in Group D for final statistical analysis. Evaluable patients are those who complete the planned PK sample collection on Cycle 2 Day 1 and have no lorlatinib dose modification until completion of Cycle 2 Day 1 PK evaluation. Patients who are not evaluable for PK will be replaced.

Each patient will be treated with repeated oral once daily doses of lorlatinib in 21-day cycles until disease progression, patient refusal, or unacceptable toxicity occurs.

The planned dosing schedule for each treatment group is as follows (Table 4):

	Group B	Group C	Group D	Group A1	Group A2
Hepatic Function	Mild	Moderate	Severe	Normal	Normal
Starting Lorlatinib Dose	100 mg QD	50 mg QD or otherwise determined in the first stage	determined based on preliminary safety and PK data	100 mg QD	the same dose as Group C at the second stage
Lorlatinib Dose After PK Assessment	100 mg QD	50 mg QD or otherwise determined in the first stage	determined based on preliminary safety and PK data	100 mg QD	100 mg QD

Table 4.Lorlatinib Dosing Schedule

The dose schedule may be modified as necessary for individual patients according to tolerability (see Table 6 for detailed dose modification strategy).

For Group C, a two-stage enrollment will be applied.

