# **Adverse Events**

Adverse Events (AEs) will be coded by system organ class (SOC) and preferred term according to Medical Dictionary for Regulatory Activities (MedDRA) terminology. AE severity will be graded according to NCI Common Terminology Criteria for Adverse Events (CTCAE) version 4.0.3.

A listing of all AEs including detailed information collected for each AE (description of event, onset date/time, duration, seriousness, severity, relationship to study drug, action taken, clinical outcome) will be presented.

The number and percentage of patients who experienced any: AE, serious AE (SAE), treatment related AE, and treatment related SAE will be summarized. Emphasis in the analyses will be placed on AEs classified as treatment emergent. The analyses will summarize AEs both on the entire study period and by cycle (Cycle 1 and Cycles beyond 1).

Additional summaries of adverse events (AE) and of other safety data will be presented in tabular and/or graphical format and summarized descriptively, as appropriate.

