#### Laboratory Test Abnormalities

The number and percentage of patients who experienced laboratory test abnormalities will be summarized according to worst toxicity grade observed for each laboratory assay. The analyses will summarize laboratory tests both on the entire study period and by cycle (Cycle 1 and Cycles beyond 1). Shift tables will be provided to examine the distribution of laboratory toxicities.

For laboratory tests without CTCAE grade definitions, results will be categorized as normal, abnormal, or not done.

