5.5. Safety Summaries and Analyses

Summaries and analyses of safety parameters will be provided based on the on-treatment period unless otherwise specified, by hepatic function group for the Safety Analysis Set. For all safety analyses, only descriptive methods will be used without any formal statistical testing.

The on-treatment period is defined as the time from the first dose of study treatment through and including 28 days after last dose or start of new anti-cancer drug therapy, whichever occurs first [minimum (28 days + last dose of study treatment, start day of new anti-cancer drug therapy - 1 day)]. Adverse events occurring on the same day as the first dose of study treatment will be considered to have occurred during the on-treatment period. All other safety assessments which occur on the same day as the first dose of study treatment will be considered baseline assessments.

Safety data collected outside the on-treatment period as described above will be listed but not summarized.

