5.5.1. Adverse Events

An adverse event is considered treatment emergent if:

- the event occurs for the first time during the on-treatment period and was not seen prior to the start of treatment (Cycle 1 Day 1), or
- the event was seen prior to the start of treatment but increased in severity during the on-treatment period.

Adverse Events (AEs) will be graded by the investigator according to the Common Terminology Criteria for Adverse Events (CTCAE) version 4.03 and coded using the Medical Dictionary for Regulatory Activities (MedDRA). The focus of AE summaries will be on Treatment Emergent Adverse Events, those with initial onset or increasing in severity after the first dose of study medication. The number and percentage of patients who experienced any AE, serious AE (SAE), treatment related AE, and treatment related SAE will be summarized according to worst toxicity grades. The summaries will be presented by hepatic function group, by system organ class and preferred term.

Patients who withdraw from study treatment because of an AE will be listed. Patient discontinuation will be determined from the end of treatment (EOT) evaluation (where reason for termination is "Adverse Event") and the specific AE(s) will be determined from the AE CRF page (where action taken is "Withdrawn from Study" or action taken for study drug is "Permanently Discontinued").

Adverse events associated with permanent discontinuation of the study drug or with temporary discontinuation/dose reduction will also be summarized (taking into consideration the action taken from the CRF AE page).

Clustered adverse events will be summarized by maximum CTCAE grade and causality (all-causality and treatment-related) together with other adverse events. Adverse Events pertaining to each cluster will be summarized separately, by cluster. The clustered events are described in a list in the product's Safety Narrative Plan maintained by the Sponsor.

All causality and treatment-related SAEs will be summarized by MedDRA SOC, preferred term and maximum CTCAE grade. Patients who experienced a SAE during the SAE reporting period will be listed for all the patients in the safety analysis set. A summary of SAEs by preferred term, maximum CTCAE grade will be presented.

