5.5.2. Laboratory Data

Hematology, biochemistry, and lipid results will be programmatically graded according to the NCI CTCAE Version 4.03.

The number and percentage of patients who experienced laboratory test abnormalities will be summarized according to worst toxicity grade observed on treatment for each lab assay. Worst case is defined as the maximum post-baseline CTCAE grade using scheduled and unscheduled visits. The analyses will summarize laboratory tests on the entire study period. Shift tables of baseline grade by maximum post-baseline CTCAE grade will also be presented.

Patients who developed Grade \geq 3 toxicity will be listed.

An evaluation of Drug-Induced Serious Hepatotoxicity (eDISH) plot will also be created, by graphically displaying post-baseline:

- peak serum ALT(/ULN) vs peak total bilirubin (/ULN) including reference lines at ALT=3×ULN and total bilirubin=2×ULN.
- peak serum AST(/ULN) vs peak total bilirubin (/ULN) including reference lines at AST=3×ULN and total bilirubin=2×ULN.

In addition, a listing of all TBILI, ALT, AST and ALP values for patients with a post-baseline TBILI $\ge 2 \times ULN$, ALT $\ge 3 \times ULN$ or AST $\ge 3 \times ULN$ will be provided.

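### The SAP omits the by-cycle adverse event and laboratory summaries that Protocol 9.4 requires, leaving crude percentages over on-treatment periods of unequal length; hepatic groups treated for less time can look safer.

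*SAP*

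**What the plan says.** On AEs, Protocol 9.4 says: "The analyses will summarize AEs both on the entire study period and by cycle (Cycle 1 and Cycles beyond 1". On laboratory abnormalities it says: "The analyses will summarize laboratory tests both on the entire study period and by cycle (Cycle 1 and Cycles beyond 1".

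The SAP differs on both.

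- **Default (SAP 5.5):** "Summaries and analyses of safety parameters will be provided based on the on-treatment period unless otherwise specified, by hepatic function group".
- **Laboratory data (SAP 5.5.2):** the corresponding sentence is only "The analyses will summarize laboratory tests on the entire study period".
- **AEs (SAP 5.5.1):** "The number and percentage of patients who experienced any AE, serious AE (SAE), treatment related AE, and treatment related SAE will be summarized", by worst grade, and "The summaries will be presented by hepatic function group, by system organ class and preferred term". Cycle is not part of the layout.
- **Window (SAP 5.5):** "The on-treatment period is defined as the time from the first dose of study treatment through and including 28 days after last dose", or to the day before new anti-cancer drug therapy if that comes first.

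Under Protocol 3.1, patients are treated "in 21-day cycles until disease progression, patient refusal, or unacceptable toxicity occurs", so the window has no fixed length. SAP 5.4.3 tabulates treatment duration, days on drug and relative dose by hepatic group, but no AE or laboratory summary uses time as a denominator. SAP 2 allows the SAP to modify the protocol's plans and describes it as a supplement to the protocol. Neither the text nor the version table mentions the by-cycle summaries.

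**The concern.** The effect of hepatic impairment on safety is a secondary objective, and the side-by-side AE and laboratory tables are its main evidence. A percentage of patients with at least one event grows with time observed whenever events keep accruing. If one hepatic group stays on drug for less time, its percentage is lower for that reason alone. Worst post-baseline laboratory grade behaves in the same way.

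The Cycle 1 table in Protocol 9.4 would put all groups on a common 21-day footing. The SAP plans no substitute: no fixed-window summary, no rate per person-time and no time to first event.

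The C versus A2 contrast has a second problem. Protocol Table 4 moves A2 to 100 mg QD after the Cycle 2 Day 1 PK assessment, while Group C stays on its own schedule. Whole-period percentages in A2 can then cover two doses. The rule in SAP 5 that splits a hepatic group by dose level separates patients, not periods within a patient, so it does not deal with this.

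**Working it through.** The plan gives no AE rate and no time on drug, so it has no figure to reproduce on this point. The rates and durations below are assumptions, shown as a range.

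**Step 1: length of the window.** From SAP 5.5, a patient who stops after *n* 21-day cycles is observed for T = 21n + 28 days, absent new therapy or death. That gives 70 days for 2 cycles, 112 for 4 and 196 for 8.

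**Step 2: whole-period percentage.** Let *p* be the Cycle 1 risk and assume a constant daily hazard h = −ln(1 − p)/21. Then P = 1 − exp(−hT) = 1 − (1 − p)^(T/21). For p = 10% and 2 cycles, P = 1 − 0.9^(70/21) = 29.6%.

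With the same hazard whatever the duration:

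| Cycle 1 risk | 2 cycles | 4 cycles | 8 cycles |
|---|---|---|---|
| 5% | 15.7% | 23.9% | 38.0% |
| 10% | 29.6% | 43.0% | 62.6% |
| 20% | 52.5% | 69.6% | 87.5% |

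Between 2 and 8 cycles the gap is 22 to 35 percentage points with no true difference. Between 4 and 8 cycles it is 14 to 20 points (38.0 − 23.9 = 14.1; 62.6 − 43.0 = 19.6; 87.5 − 69.6 = 17.9). A Cycle 1 table shows equal risks in every row.

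**Step 3: a true excess in the shorter-treated group** (2 cycles, against 8 cycles at the base hazard):

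| Base Cycle 1 risk | Hazard doubled: whole period | Hazard doubled: Cycle 1 | Hazard tripled: whole period |
|---|---|---|---|
| 5% | 29.0% vs 38.0% | 9.8% vs 5% | 40.1% vs 38.0% |
| 10% | 50.5% vs 62.6% | 19.0% vs 10% | 65.1% vs 62.6% |
| 20% | 77.4% vs 87.5% | 36.0% vs 20% | 89.3% vs 87.5% |

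A doubling is reversed in the whole-period table and correctly ordered in the Cycle 1 table. At a tripling the whole-period figures are about level.

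**Step 4: stopping times that vary between patients.** With exponential time on drug at rate λ = ln 2/median, P = 1 − exp(−28h) × λ/(λ + h). At p = 10%, medians of 42 and 168 days give 33.4% and 60.8%, so the gap does not depend on everyone stopping on the same day.

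**Step 5: rate per person-time.** Count patients with an event and divide by time to first event or end of window. Under the model this estimates h whatever T is. At p = 10%, h = 0.10536/21 = 0.00502 per day, or 0.00502 × 30.44 = 0.153 per patient-month in both groups. With a doubled hazard it is 0.305 against 0.153.

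**Step 6: where the distortion is small.** If every event falls in the first 21 days, the percentages do not depend on duration. The 28 days after last dose cover that window for anyone who stops early, unless new therapy or death intervenes.

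**Step 7: dose.** B and A1 both start at 100 mg QD, and A2 starts at the Group C second-stage dose. The A2 switch comes after Cycle 2 Day 1, so Cycle 1 lies before it. Cycle 1 is therefore matched on both time and starting dose for B versus A1 and for second-stage C versus A2. If Group C's dose is set at 100 mg QD, A2 is not enrolled and the mixing does not arise.

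**The case against.** **For AEs the SAP is silent rather than contrary.** It calls itself a supplement, so the AE commitment in Protocol 9.4 can be read as still in force. This stands: a reader might infer that the AE split was deliberately removed, and the documents do not show that. The laboratory sentence does lack the by-cycle part, however, so the SAP should state what applies to both.

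**The direction is assumed.** A reader might infer that impaired groups will stop earlier and so will look safer. The documents do not support this. They give no durations, and controls with normal liver function are also patients without effective standard options who may gain no benefit from lorlatinib, so they too may progress early. Early-onset events shrink the effect, and patients who stop for toxicity already count as having an event. What stands is that shorter-treated groups can look safer, not that they will.

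**Group D.** A reader might take it as a clean fixed-dose example. It is not. Protocol Table 4 leaves its dose, before and after PK assessment, to be determined from preliminary data, and it has no designated control unless it shares Group C's dose and so half of A2.

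**Exposure is visible and safety is descriptive.** Duration is tabulated by group, AE onset dates are listed, and ECG and vital signs are summarized by nominal visit. This confines the point to AE and laboratory tables. It does not correct the percentages, which readers will compare directly.

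**Groups are small.** With 8 patients, 3/8 has an exact 95% interval of about 9–76% and 6/8 about 35–97%. This is true, but it limits every table equally and does not justify adding a systematic distortion.

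**Neither document promises exposure-adjusted rates or gives Cycle 1 priority.** This also stands. Making Cycle 1 the only between-group comparison would go beyond Protocol 9.4 and play down later toxicity.

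**Conclusion.** The concern holds in a limited form. The SAP departs from Protocol 9.4 by omission, explicitly for laboratory data and by silence for AEs, and records no reason. The remaining summaries are crude percentages over unequal periods.

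Their possible distortion is conditional on three things: time on drug differs between hepatic groups, events continue to accrue after Cycle 1, and any true excess is not large enough to overcome the shorter observation. Under the assumed constant hazards, 2 against 8 cycles moves the percentages by 22 to 35 points with no true difference and reverses a doubling. A tripling roughly cancels it. None of these figures predicts this trial.

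The dose mixing in C versus A2 follows from the dosing schedule itself and applies whenever A2 is enrolled at a dose other than 100 mg QD. This is a should-fix: it bears on a secondary, descriptive objective and is easily corrected before the tables are produced.

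**What to change.** In SAP 5.5.1 and 5.5.2:

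1. Restore AE and laboratory abnormality tables for Cycle 1 and for Cycles beyond 1, by hepatic function group and by dose level within group as SAP 5 already requires. Show them alongside the whole-period tables, not in place of them. State that Cycle 1 is the window matched on time and starting dose.
2. For the whole on-treatment period and for Cycles beyond 1, add the number of patients with an event per patient-month at risk. Count time to first event or end of window. The later-cycle table needs this because its follow-up is also unequal.
3. If the sponsor prefers not to restore the split, record the departure from Protocol 9.4 and the reason in the SAP.

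The cost is SAP wording, a date filter on existing tables and one extra column. Dosing, onset and sampling dates are already collected. The downside is a few more tables, and the rates will be imprecise in groups of about 6 to 8 patients.

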- 14. **12-Lead ECG**: Triplicate ECG will be performed at screening, times 0 (predose) 1, 2, 4, 10 and 24 hours post dose on Cycle 1 Day 1 and Cycle 2 Day 1, predose on days 8 and 15 in cycle 1, and at the end of treatment. At each time point, 3 consecutive 12-lead ECGs are to be performed approximately 2 minutes apart. The ECG must occur prior to any blood sample collections or venipuncturing or collection of vital signs. All ECGs scheduled at 0 hours must be collected prior to dosing. All efforts should be made to ensure the ECG collections completed within 15 minutes prior to the PK collection if they are planned at the same time. Additional ECGs may be collected as clinically indicated. Single reading ECG will be collected pre-dose on Day 1 of Cycle 3 and every cycle thereafter.
- 15. LVEF Assessment: Echocardiogram or MUGA to be performed at Screening, at pre-dose (0 hour) on Cycle 1 Day 1 (not required if screening LVEF was obtained within 7 days prior to Cycle 1 Day 1) and on Day 1 of every other cycle thereafter, and at the EOT visit. The same method should be used at each time point.
- 16. Enrollment: Enrollment number and treatment group allocation assigned by Pfizer Inc based on AST and total bilirubin values.
- 17. **Tumor Assessments**: Tumor assessments will include all known or suspected disease sites. Imaging may include CT or MRI scans of chest, abdomen, and pelvis. Brain scans and bone scans will be performed at screening if disease is suspected and on study as appropriate to follow disease. The Investigator evaluation will be used for response analysis according to RECIST v1.1. Tumor assessment should be repeated at the end of treatment visit if more than 6 weeks have passed since the last evaluation.

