#### 1.2.1.2.1.6. Study B7461008

Study B7461008 is a completed Phase 1 study in 24 healthy volunteers, designed to evaluate the effect of rabeprazole and food on the pharmacokinetics of lorlatinib and to assess the relative bioavailability (BA) of an oral solution of lorlatinib to the tablet formulation of lorlatinib.

Results indicate that a high fat meal has no effect on the systemic exposure of lorlatinib. Similarly, proton pump inhibitor (PPI) rabeprazole had only a marginal effect on the systemic exposure of lorlatinib. Based on these results, the current recommendation is that lorlatinib can be given without regard to food or any acid reducing agents such as PPIs or H2-receptor antagonists.

Safety data from this study recently identified asymptomatic PR prolongation. In one healthy volunteer, the PR interval prolongation was associated with one episode of transient second degree atrioventricular (AV) block (Mobitz type 1; Wenkebach). Subsequently, retrospective review of patients in the clinical study B7461001, found one patient with the PR interval prolongation that may have been associated with the progression of pre-existing AV block to complete heart block. When the complete heart block was identified, the patient was immediately evaluated and subsequently treated by placement of an implanted pacemaker.

In response to the observation of PR interval prolongation, data from all available human studies (approximately 100 patients in clinical study B7461001 and 45 in single dose healthy volunteer studies) were reviewed. Additional instances were identified of asymptomatic increases in the PR interval (>200 msec), usually most notable at the time of  $C_{max}$  (1-2 hours post-dose) in healthy volunteers. Of note, the subjects with a PR interval >200 msec were generally those with a baseline values at the upper end of the normal range.

The electrocardiogram (ECG) changes appear limited to the PR interval, with no impact on QRS or QT intervals. This impact on the PR interval is supported by preclinical animal studies, as described in the current IB.

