#### 9.4.1. Electrocardiogram

The analysis of ECG results will be based on patients in the safety analysis set with baseline and on-treatment ECG data.

ECG measurements (an average of the triplicate measurements) will be used for the statistical analysis and all data presentations. Any data obtained from ECGs repeated for safety reasons after the nominal time-points will not be averaged along with the preceding triplicates. Interval measurements from repeated ECGs will be included in the outlier analysis (categorical analysis) as individual values obtained at unscheduled time points.

QT intervals will be corrected for heart rate (HR) (QTc) using standard correction factors (ie, Fridericia's (default correction), Bazett's, and possibly a study-specific factor, as appropriate). Data will be summarized and listed for QT intervals, HR, RR intervals, PR intervals, QRS intervals, and QTcF (and other correction factors, eg, QTcB as appropriate) by hepatic function and dose. Individual QT (all evaluated corrections) intervals will be listed by study hepatic function, time and dose. The most appropriate correction factor will be selected and used for the following analyses of central tendency and outliers and used for the study conclusions. Descriptive statistics (n, mean, median, standard deviation, minimum, and maximum) will be used to summarize the absolute corrected QT interval and changes from baseline in corrected QT after treatment by hepatic function, dose and time point. For each patient and by treatment, the maximum change from baseline will be calculated as well as the maximum post-baseline interval across time-points. Categorical analysis will be conducted for the maximum change from baseline in corrected QT and the maximum post-baseline QT interval.

Shift tables will be provided for baseline vs worst on treatment corrected QT (one or more correction methods will be used) using maximum CTCAE Grade. Shift tables will also be provided for ECG abnormality at baseline vs. on treatment (yes, no, not done: (n, %)). Patients experiencing clinically relevant morphological ECG changes will be summarized (including frequency and percentage).

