3.3. Baseline Variables

The date of first dose (start date) of study treatment is the earliest date of non-zero dosing of the study drug. The date of last dose of study treatment is the latest date of non-zero dosing of the study drug.

No windowing will be applied when defining baseline. Any deviations from the protocol specified window will be documented as protocol deviations.

For efficacy analyses the last assessment prior to randomization will serve as the baseline assessment.

For safety (including Eastern Cooperative Oncology Group (ECOG) performance status) the last assessment performed on or prior to date of the first dose of study treatment will serve as the baseline assessment. If there are no observations meeting these criteria, then baseline is considered missing.

Triplicate ECGs are collected; therefore the baseline for each ECG measurement is the average of the pre-dose measurements on the baseline day. Unscheduled assessments will not be included in the calculation of the average.

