5.5.4. Electrocardiogram

A triplicate 12-lead will be used for all ECG assessments.

All patients require a triplicate ECG measurement at screening and at each scheduled time point during treatment. A mean score is calculated for the replicate measurements having the same nominal visit, and will be reported.

QT, RR, HR, PR, QRS, QTcF (Fridericia correction), and QTcB (Bazett's correction) data will be provided by sites on the ECG page of the CRF.

The analysis of ECG results will be provided for safety analysis set patients with baseline and on-treatment ECG data by hepatic group and for each nominal visit over time. ECG measurements collected closest prior to the first dose of study drug will be used as the baseline ECG for analysis.

ECG measurements (an average of the triplicate measurements) will be used for the statistical analysis and all data presentations. Any data obtained from ECGs repeated for safety reasons after the nominal time points will not be averaged along with the preceding triplicates. Interval measurements from repeated ECGs will be included in the outlier analysis as individual values obtained at unscheduled time points.

Descriptive statistics (n, mean, median, standard deviation, minimum, and maximum) will be used to summarize the absolute value and changes from baseline in QT, QTcF, QTcB, HR, RR, PR, QRS after treatment by hepatic group and nominal visit.

The number (%) of subjects with maximum post dose QTc values and maximum increases from baseline in the following categories will be tabulated:

| Absolute Value (msec) | ≥450 -<480 |
|------------------------|------------|
| | ≥480 -<500 |
| | ≥500 |
| Absolute Change (msec) | 30-<60 |
| | ≥60 |

The number (%) of subjects with maximum post-dose PR interval values and maximum increases from baseline in the following categories will be tabulated:

| Absolute Value (msec) | <160 |
|-------------------------------|-------------|
| | ≥160 - <180 |
| | ≥180 - <200 |
| | ≥200 - <220 |
| | ≥220 - <240 |
| | ≥240 - <260 |
| | ≥260 |
| Absolute Change (msec) | 40-<60 |
| | ≥60-<80 |
| | ≥80 |
| Relative Change from baseline | >25% |

Shift tables will be provided for baseline vs worst on study PR using the categories in the above table. The effect of drug concentrations on QTc change (and PR interval) from baseline will be explored graphically.

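### SAP 5.5's same-day baseline rule has no pre-dose limit, so read literally it captures the Cycle 1 Day 1 post-dose ECGs and conflicts with the ECG-specific text

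*SAP*

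**What the plan says.** SAP 5.5 sets the scope of the safety summaries: "Summaries and analyses of safety parameters will be provided based on the on-treatment period unless otherwise specified". It then gives the period: "The on-treatment period is defined as the time from the first dose of study treatment through and including 28 days after last dose", cut short if a new anti-cancer drug is started. Adverse events on the day of first dose count as on-treatment. For everything else: "All other safety assessments which occur on the same day as the first dose of study treatment will be considered baseline assessments". Safety data outside the on-treatment period are listed only.

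The Protocol Schedule of Activities (footnote 14) calls for triplicate ECGs at "times 0 (predose) 1, 2, 4, 10 and 24 hours post dose on Cycle 1 Day 1 and Cycle 2 Day 1", plus pre-dose triplicates on Days 8 and 15 of Cycle 1.

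The ECG-specific text is worded differently:
- SAP 3.3: "the baseline for each ECG measurement is the average of the pre-dose measurements on the baseline day".
- SAP 5.5.4 takes the ECG closest before the first dose as baseline. It analyses patients who have both baseline and on-treatment ECG data, and tabulates the largest post-dose QTc and PR values and increases.
- Protocol 9.4.1 uses the Cycle 1 Day 1 pre-dose ECG as baseline and summarises "changes from baseline in corrected QT after treatment by hepatic function, dose and time point".

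**The concern.** An ECG is a safety assessment and is not an adverse event, so the same-day sentence covers it. Nothing in that sentence separates the pre-dose tracing from those taken 1, 2, 4 and 10 h later on the same date. SAP 5.5.4 asks for on-treatment ECG data but does not redefine on-treatment for ECGs, so a programmer would look to SAP 5.5 for the definition and meet the same-day rule there.

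The early readings matter because PR prolongation is the recognised ECG effect of the drug. Protocol 1.2.1.2.1.6 reports "asymptomatic increases in the PR interval (>200 msec), usually most notable at the time of" peak concentration, 1 to 2 h after dosing, in healthy volunteers from single-dose studies. If the first-dose readings at those hours were classed as baseline, the maximum PR and QTc tables, the changes from baseline, the PR shift table and the concentration-ECG plots could all omit them. The effect of hepatic impairment on safety is a secondary objective, and these summaries are part of the evidence for it.

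**Working it through.** No power, alpha or sample-size figure is involved. The check is a count of scheduled time points and a comparison of the texts.

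**Inputs** (Schedule of Activities footnote 14 and the sampling schema): ECGs at 0, 1, 2, 4, 10 and 24 h on Cycle 1 Day 1 and again on Cycle 2 Day 1; pre-dose ECGs on Cycle 1 Days 8 and 15.

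**Which readings share the date of first dose.** A reading at h hours falls on the same date if dosing clock time + h < 24:00. The 10 h reading does so only if dosing is before 14:00. The 4 h reading does so if dosing is before 20:00. The 24 h reading is always on the next date. The documents fix no clock time for dosing, so both cases are shown.

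**Totals.** Post-dose points on Cycle 1 Day 1: 5. Post-dose points over both serial days: 5 + 5 = 10. Readings at 1 and 2 h over both days: 2 + 2 = 4. Triplicate points after the first dose through 24 h of Cycle 2 Day 1: 5 + 2 + 6 = 13.

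| Scheduled ECG time points | Total | Classed as baseline, dosing before 14:00 | Classed as baseline, dosing from 14:00 and before 20:00 |
|---|---|---|---|
| Cycle 1 Day 1, post-dose | 5 | 4 (80%) | 3 (60%) |
| Serial post-dose, both days | 10 | 4 (40%) | 3 (30%) |
| 1 and 2 h readings, both days | 4 | 2 (50%) | 2 (50%) |
| All triplicates, first dose to Cycle 2 Day 1 at 24 h | 13 | 4 (31%) | 3 (23%) |

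With dosing before 14:00, the literal rule leaves 13 − 4 = 9 on-treatment time points. With the rule limited to pre-dose readings, all 13 remain. The Cycle 2 Day 1 series is untouched either way.

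**The texts side by side:**
1. By time, the 1 to 10 h readings lie inside the on-treatment period, because it starts at the first dose. By the same-day sentence in the same paragraph, they are baseline.
2. By SAP 3.3, SAP 5.5.4 and Protocol 9.4.1, they cannot contribute to the ECG baseline value, which is pre-dose only.
3. By the maximum tables in SAP 5.5.4, they belong in the analysis, because those tables are defined on post-dose values.

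Applied together, the rules leave these readings labelled baseline, barred from the baseline value, and called for in the post-dose maxima. Under the ECG-specific rules alone, 0 time points are lost. No sentence says that same-day post-dose ECGs are excluded, and none says that they are exempt from the same-day rule.

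**The case against.** The best defence is that specific text overrides general text. SAP 5.5 opens with an exception for what is specified elsewhere, and the ECG sections have their own pre-dose baseline and ask for post-dose maxima. The same-day rule also has an ordinary purpose. Footnote 2 of the Schedule of Activities has assessments done before dosing unless otherwise indicated, so for laboratory tests, vital signs, LVEF and ECOG status the rule simply yields a pre-dose baseline. Serial ECG is the exception, and it has its own text.

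Most of this stands, and it is why loss of the readings cannot be called settled. It does not remove the conflict. The exception clause is attached to the period used for summaries, not to the same-day sentence. SAP 5.5.4 names no other period. The pre-dose baseline text says which readings form the baseline value, not how same-day post-dose readings are classed.

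A reader might also infer that SAP 5.5.4 averages pre-dose and post-dose readings together, since it says "A mean score is calculated for the replicate measurements having the same nominal visit". The documents do not support that. The same section speaks of a triplicate at each scheduled time point and of the average of the triplicate, and SAP 4.3.4 handles missing triplicates by time point. What remains is loose wording: the summaries are keyed to nominal visit, where Protocol 9.4.1 says time point.

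**Conclusion.** The point holds as a conflict between a stated rule and the ECG-specific text. If SAP 5.5 is applied as written, up to 4 of the 5 post-dose ECG time points on Cycle 1 Day 1, and 2 of the 4 scheduled 1 to 2 h readings, leave the on-treatment summaries. The count of 4 assumes dosing before 14:00. If the ECG-specific text governs, nothing is lost. Even on the literal reading, the 24 h ECG, the Day 8 and Day 15 ECGs and the whole Cycle 2 Day 1 series remain. The affected summaries are descriptive and secondary, and the primary PK analysis is not touched.

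Two stronger readings should not be drawn:
- A reader might take the planned 76 enrolled for 38 PK-evaluable patients to mean that many would have no 1 to 10 h reading left. The documents give no rate of stopping before Cycle 2 Day 1. Under Protocol 9.1, patients can also be non-evaluable through dose reduction, receiving under 80% of dose or incomplete PK collection, and such patients may still have Cycle 2 Day 1 ECGs.
- A reader might infer that the readings at risk sit at higher peaks, because Protocol Table 3 shows single-dose Cmax above multiple-dose Cmax at 100 mg (595.5/550.2 = 1.08; 695.2/576.5 = 1.21). These are geometric means with CVs of 32 to 42%, and the Phase 2 groups differ in size (19 and 26). Protocol 1.2.2 says auto-induction may differ in hepatic impairment. Group C starts at 50 mg, and the Group D dose is not yet set.

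**What to change.** Make two changes in the SAP:
1. In SAP 5.5, limit the same-day rule to non-AE safety assessments taken before the first dose.
2. In SAP 5.5.4, state that all ECGs after the first dose, including those on Cycle 1 Day 1, are on-treatment and enter the maximum post-dose, change-from-baseline, shift and concentration-ECG analyses.

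As a minor alignment, have SAP 5.5.4 summarise by nominal visit and time point, to match Protocol 9.4.1.

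The cost is a few phrases in the SAP and a matching check of the programming specification. No new data are needed: the scheduled hour of each ECG already separates pre-dose from post-dose readings.
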